8.5 Stopping rules

The study will be monitored to ensure that the occurrence of a specified set of treatment related serious adverse events (TRSAEs) that occur during the treatment period does not substantially exceed an anticipated rate. The following specified TRSAEs determined to be probably or definitely related to eltrombopag will be considered for early stopping of the study:

1. Death
2. Any Grade IV toxicity excluding readily reversible metabolic or laboratory abnormalities
3. Grade IV thrombosis/embolism

We anticipate the rate of these specified TRSAEs within the 3 month study period to be 20% or less. Following Geller et al. (12), our stopping rule is determined by a Bayesian approach. The stopping boundary for an experiment is reached if the Bayesian posterior probability that the true probability of developing one or more of the specified TRSAE's exceeds this benchmark rate of 20% is at least 90%. We take our prior distribution to be a beta distribution with parameters $(\alpha, \beta) = (0.72, 2.88)$, so that $\alpha + \beta = 3.6$ is approximately 15% of the expected sample size. The parameter are chosen so that the mean $\alpha / (\alpha + \beta) = 0.2$ as the expected proportion of specified TRSAE's and the sum $\alpha + \beta = 3.6$ as the "worth" we place on our prior clinical opinion. Practical interpretations and justifications of the Bayesian approach and the choice of the prior distributions can be found in Geller et al. Since we have seen in the past that the first few subjects to be accrued are possibly sicker than the rest of the subjects in the sample, we will start safety monitoring when 3 or more subjects have developed a TRSAE. The following table summarizes the threshold numbers for stopping the study.

Number of subjects in the experiment	Stop if the number of subjects who have developed any of the specified TRSAE's reaches:
≤ 5	3
≤ 9	4
≤ 13	5
≤ 16	6
≤ 20	7
≤ 24	8
≤ 28	9
≤ 33	10

We investigated the performance of the above stopping rule by a simulation study. In each simulation run, we generated a study with 33 independent Bernoulli trials, each had a probability p for having TRSAE and $q=1-p$ for not having TRSAE and compared the TRSAE outcomes with the above stopping boundary to determine whether the study was stopped. We repeated the simulation 100,000 times and computed the proportion of stopped studies (i.e. “number of stopped studies”/100,000) which were stopped using the above stopping rule. The following table summarizes the proportions of stopped studies under a number of scenarios for p :

Probability of TRSAE = p	0.10	0.20	0.25	0.30	0.40
Proportion of Stopped Studies	1.8%	22.4 %	43.9 %	66.7 %	93.9 %
Average number of subjects	24.7	22.4	20.3	17.6	12.0
Average number TRSAEs	3.2	5.7	6.2	6.1	5.0

These results suggest that our stopping rule has a low probability stopping a study when the proportion of specified TRSAE is below the benchmark value of 20%, and the probability of stopping a study is high when the true proportion of TRSAE exceeds this benchmark value. Based on these results, we believe that our Bayesian stopping rule has satisfactory statistical properties.

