- The incidence of SAEs was 0% and 14% in REPEAT and EXTEND, respectively and discontinuations due to AEs were $\leq 6\%$ across the 2 studies

- 2/66 (3%) subjects in REPEAT and 8/109 (7%) subjects in EXTEND developed elevations of hepatobiliary laboratory values. The majority of events were asymptomatic and resolved following drug discontinuation.
- The proportion of Asians who had hepatobiliary laboratory abnormalities (transaminases >3x ULN, bilirubin \geq 1.5x ULN or ALP \geq 1.5x ULN) was 15.8%, 16.7%, and 20.8%, as compared to 10.2%, 7.5%, and 4.5% of White-Caucasian subjects, in TRA100773A, TRA100773B, and EXTEND, respectively. High plasma eltrombopag concentrations were noted in 2 subjects who had ALT and AST elevations (>3x ULN).
- Four eltrombopag treated subjects developed thromboembolic events (4 in EXTEND, none in REPEAT). Although risk factors were present in all subjects, a causal relationship with eltrombopag cannot be ruled out.
- With the exception of the hepatobiliary findings in Asian subjects, no clinically meaningful differences in the safety profile of eltrombopag were found with regard to age, sex and race.

TRA100773A (chronic ITP Study): A double blind randomized, placebo controlled, Phase II, parallel group study designed to investigate the efficacy, safety, tolerability, pharmacokinetics and pharmacodynamics of eltrombopag administered at 30 mg, 50 mg and 75 mg as oral tables compared with placebo once daily for 6 weeks in 117 subjects with previously treated, chronic ITP.

TRA100773B (chronic ITP study) A double-blind, randomized, placebo-controlled Phase III study to assess the safety and efficacy of 50 mg eltrombopag administered as an oral tablet once daily for up to 6 weeks in 114 subjects who were previously treated for chronic ITP and who had a platelet count of less than 30,000/uL.

The primary analysis of this endpoint was performed on a dataset which classified subjects as either responders or non-responders (primary dataset). For this primary analysis of response, only on-therapy platelet counts were included. Responders either achieved a platelet count of \geq 50 K/uL (from a baseline platelet count of <30 K/uL) at the Day 43 Visit, or achieved a platelet count >200 GK/uL and discontinued study medication prior to Day 43; and non-responders either did not achieve a platelet count \geq 50 K/uL at Day 43 or discontinued treatment prior to Day 43 for any reason other than a platelet count >200 K/uL.

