9 DATA AND SAFETY MONITORING

9.1 Data and Safety Monitoring

Principal Investigator: Accrual, efficacy and safety data will be monitored by the Principal Investigator, [name].

NIH Intramural IRB. Accrual and safety data will be monitored and reviewed annually by the Institutional Review Board (IRB). Prior to implementation of this study, the protocol and the proposed patient consent and assent forms will be reviewed and approved by the properly constituted Institutional Review Board (IRB) operating according to Title 45 CFR 46. This committee will also approve all amendments to the protocol or informed consent, and conduct continuing annual review so long as the protocol is open to accrual or follow up of subjects.

NHLBI DSMB: The NHLBI Data safety and Monitoring Board will review the protocol at 6 to 12 month intervals. A progress report will be forwarded to the DSMB at these times and their recommendations will be expeditiously implemented. The DSMB may recommend early termination of the study for considerations of safety and efficacy.

Monitoring: As per ICH-GCP 5.18 and 21 CFR 312.50, clinical protocols are required to be adequately monitored by the study sponsor. The monitoring of this study will be conducted by Clinical Research Associates (CRAs)/Monitors employed by an independent contract organization working under an agreement with NHLBI to monitor aspects of the study in accordance with the appropriate regulations and the approved protocol. The objectives of a monitoring visit will be: 1) to verify the existence of signed informed consent form (ICF) and documentation of the ICF process for each monitored subject; 2) to verify the prompt and accurate recording of all monitored data points, and prompt reporting of all SAEs; 3) to compare abstracted information with individual subjects' records and source documents (subject's charts, laboratory analyses and test results, physicians' progress notes, nurses' notes, and any other relevant original subject information); and 4) to help ensure investigators are in compliance with the protocol. The monitors also will inspect the clinical site regulatory files to ensure that regulatory requirements (Office for Human Research Protections-OHRP) and applicable guidelines (ICH-GCP) are

being followed. During the monitoring visits, the investigator (and/or designee) and other study personnel will be available to discuss the study progress and monitoring visit.

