2	Unlikely (must have two)	In general, this category can be considered applicable to those adverse events which, after careful medical consideration at the time they are evaluated, are judged to be unrelated to the test drug. An adverse event may be considered unlikely if or when: 
 1. It does not follow a reasonable temporal sequence from administration of the test drug. 2. It could readily have been produced by the subject's clinical state, environmental or toxic factors, or other modes of therapy administered to the subject. 3. It does not follow a known pattern of response to the test drug. 4. It does not reappear or worsen when the drug is re-administered.
3	Possibly (must have two)	This category applies to those adverse events for which, after careful medical consideration at the time they are evaluated, a connection with the test drug administration appears unlikely but cannot be ruled out with certainty. An adverse event may be considered possibly related if or when: 
 1. It follows a reasonable temporal sequence from administration of the test drug. 2. It could not readily have been produced by the subject's clinical state, environmental or toxic factors, or other modes of therapy administered to the subject. 3. It follows a known pattern of response to the test drug.

4	Probably (must have three)	
This category applies to those adverse events for which, after careful medical consideration at the time they are evaluated, are felt with a high degree of certainty to be related to the test drug. An adverse event may be considered probably related if or when:
 
 1. It follows a reasonable temporal sequence from administration of the test drug. 2. It could not be reasonably explained by the known characteristics of the subject's clinical state, environmental or toxic factors, or other modes of therapy administered to the subject. 3. It disappears or decreases on cessation or reduction in dose. There are important exceptions when an adverse event does not disappear upon discontinuation of the drug, yet drug-relatedness clearly exists (e.g., bone marrow depression, fixed drug eruptions, tardive dyskinesia). 4. It follows a known pattern of response to the test drug.

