5	Definitely (must have all)	
This category applies to those adverse events which, the Investigator feels are incontrovertibly related to test drug. An adverse event may be assigned an attribution of definitely related if or when:
 
 1. It follows a reasonable temporal sequence from administration of the test drug. 2. It could not be reasonably explained by the known characteristics of the subject's clinical state, environmental or toxic factors, or other modes of therapy administered to the subject. 3. It disappears or decreases on cessation or reduction in dose with re-exposure to drug. (Note: this is not to be construed as requiring re-exposure of the subject, however, a category of definitely related can only be used when a recurrence is observed.) 4. It follows a known pattern of response to the test drug.

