9.2.3 Serious Adverse Events Management

Serious adverse events will be attributed as definitely (clearly related to the research), probably (likely related to the research), possibly (may be related to the research), unlikely (doubtfully related to the research) and unrelated (clearly not related to the research).

Treatment related SAEs (TRSAEs) are those attributed as definitely, probably, or possibly related that will be monitored and considered for early stopping of the study according to statistically determined criteria. These include death and any grade IV toxicity considered to be probably or definitely related to study medication. [name] will serve as the independent monitor who reviews the attribution of TRSAEs.

Hospitalizations for administrative issues (to receive a transfusion) or upgrading to ICU for routine monitoring will not be reported as an SAE.

Duration of Serious Adverse Event collecting and reporting: The collection of SAEs will begin on the first day of initiation of the study drug and will continue along as the subject is on study.

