9.2.4.1 Reporting Timeframes to IRB Chair, Clinical Director, and/or IRB

Serious Events

Reports to the IRB and CD: The PI must report Serious UPs, and Serious PDs to the IRB and CD as soon as possible but not more than 7 days after the PI first learns of the event using the IRB system or other approved formats.

Reports to the CD: The PI must report all SAEs that do not meet the definition of UP to the CD not more than 14 days after the PI first learns of the event using via email.

Non-serious Events

Reports to the IRB and CD: The PI must report all UPs that are not Serious to the IRB and CD, and PDs that are not Serious to the IRB, not more than 14 days after the PI first learns of the event using the IRB system or other approved formats.

Deaths

The PI must report all deaths (that are not UPs) to the CD as soon as possible, but not more than 7 days after the PI first learns of the event.

9.2.4.2 At continuing review, the PI will provide to the IRB a summary of:

- All UPs
- All PDs
- All AEs (except for those granted a waiver of reporting)
- If, while preparing the continuing review, the PI identifies a greater frequency or level of severity of expected adverse events than was previously identified in the protocol or investigational brochure (IB), these should be reported separately as a UP. If such an observation occurs before the time of continuing IRB review, it should be reported to the IRB and CD as a UP in the time frames noted above, and summarized at the time of continuing review.

Exclusions to data reporting:

The following Adverse Events will be captured only in the source documents and will not be reported to the IRB at the time of continuing review.

- Laboratory values that do not meet the definition of AE listed in Section 9.2.2.
- All grade 1 events listed as expected in the investigator's brochure, package insert, and/or anticipated events.

9.2.4.4 NHLBI DSMB:

All grade 4 TRSAEs and reports of serious adverse events that are unexpected and thought to be related to the experimental drug will also be forwarded immediately to the Data and Safety Monitoring Board (DSMB). A summary of events will be included in DSMB reports for review by the DSMB.

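### The attribution criteria leave a death only one narrow route into the 8.5 stopping count, and 9.2.4.4 does not name deaths for immediate DSMB notice

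*Combined protocol and SAP*

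**What the plan says.** **Stopping count.** Section 8.5 lists death, grade IV toxicity (with exclusions) and grade IV thrombosis/embolism, and limits the count by attribution: "The following specified TRSAEs determined to be probably or definitely related to eltrombopag will be considered for early stopping of the study".

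**Section 9.2.3** is not consistent on the threshold. One sentence reads: "Treatment related SAEs (TRSAEs) are those attributed as definitely, probably, or possibly related that will be monitored and considered for early stopping". The next reads: "These include death and any grade IV toxicity considered to be probably or definitely related to study medication". An independent monitor reviews the attribution.

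**Attribution table (9.2.2).** *Probably* requires three of four criteria: reasonable timing, no reasonable explanation in the patient's clinical state or other treatment, dechallenge ("It disappears or decreases on cessation or reduction in dose"), and a known pattern of response to the drug. The dechallenge criterion carries a note that some events persist although they are clearly drug-related, with examples. *Definitely* requires all four, with re-exposure, and "a category of definitely related can only be used when a recurrence is observed". *Possibly* requires two of timing, no ready explanation and known pattern.

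**DSMB notice.** Section 9.2.4.4 forwards immediately: "All grade 4 TRSAEs and reports of serious adverse events that are unexpected and thought to be related to the experimental drug". Otherwise, under 9.1, "The NHLBI Data safety and Monitoring Board will review the protocol at 6 to 12 month intervals".

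**The concern.** Two of the attribution criteria presuppose a patient who survives the event: improvement after stopping, and recurrence on re-exposure. Applied to a death, they remove one of the two qualifying grades and narrow the other. The same holds for a grade IV event that does not reverse, such as a disabling stroke.

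The boundary is small early on: three events among the first five subjects. One death graded *possibly* rather than *probably* can decide whether it is crossed. The simulation in 8.5 makes no allowance for events lost through attribution.

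The thrombosis case is not remote. Section 2.4.6 reports four thromboembolic events in the EXTEND study and comments: "Although risk factors were present in all subjects, a causal relationship with eltrombopag cannot be ruled out". Those events are not described as fatal; they show only that a clot in a patient with risk factors is a realistic attribution problem for this drug.

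**Working it through.** **1. The plan's own figure.** Inputs from 8.5: the printed boundary (3 events by 5 subjects, 4 by 9, 5 by 13, 6 by 16, 7 by 20, 8 by 24, 9 by 28, 10 by 33), at most 33 subjects, and probability p per subject of at least one counted event. Method: exact binomial recursion, checking the boundary after each subject.

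| p | 0.10 | 0.20 | 0.25 | 0.30 | 0.40 |
|---|---|---|---|---|---|
| Printed stop proportion | 1.8% | 22.4% | 43.9% | 66.7% | 93.9% |
| Recomputed | 1.85% | 22.35% | 43.91% | 66.61% | 93.88% |

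The printed row reproduces to within 0.1 point.

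**2. Which criterion sets reach a countable grade.** *Probably* is met by any three of the four criteria or by all four: 4 + 1 = 5 sets. Without dechallenge, one set is left: timing, not explained, and known pattern. *Definitely* needs all four plus a recurrence, so no set is left for a death.

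**3. Fatal scenarios run through the table, without the exception.**

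| Scenario | Timing | Not explained | Known pattern | Grade |
|---|---|---|---|---|
| Clear drug toxicity of a known type | yes | yes | yes | *probably*, counted |
| Toxicity of a new type | yes | yes | no | *possibly*, not counted |
| Thrombosis with risk factors | yes | no | yes | *possibly*, not counted |
| Bleed or infection explained by the disease | yes | no | no | *unlikely*, not counted |

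The last row meets two of the criteria for *unlikely* (readily produced by the clinical state, no known drug pattern). Leaving it out is what the table intends and is not a defect.

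**4. Illustration of size.** The documents give no drug-related death rate, so the rates below are assumptions. Let g be the rate of countable grade IV events and d the rate of drug-related deaths, independent of each other. If deaths count, p = 1 − (1 − g)(1 − d). If none count, p = g. For g = 0.20 and d = 0.10, p = 1 − 0.80 × 0.90 = 0.28.

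| g | d | p if deaths count | Stop, deaths count | Stop, none count |
|---|---|---|---|---|
| 0.10 | 0.05 | 0.145 | 7.2% | 1.85% |
| 0.10 | 0.10 | 0.19 | 18.8% | 1.85% |
| 0.20 | 0.05 | 0.24 | 39.3% | 22.4% |
| 0.20 | 0.10 | 0.28 | 57.9% | 22.4% |
| 0.20 | 0.20 | 0.36 | 86.5% | 22.4% |

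The last column is the extreme in which every drug-related death is lost. Since one route to *probably* stays open, the true figure would lie between the two columns.

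**5. DSMB notice.** The first limb of 9.2.4.4 covers grade 4 events, and the grading table in 9.2.2 ends at grade 4. The second limb covers serious events that are both unexpected and thought related. Death is a serious event under 9.2.1, and an event not listed at the observed severity is unexpected there. A related, unexpected death is therefore forwarded at once. A related death that the principal investigator judges expected is not clearly in either limb.

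**The case against.** The strongest reply is that *probably* is not closed to a death. Dechallenge is one of four criteria and only three are needed. The note on persistent events gives its examples as examples, so it is not confined to them, and an independent monitor checks attribution. This stands: a reader might infer that no drug-related death could ever count, and the documents do not support that. The note does not settle the matter, though. It applies where drug-relatedness is already clear, which is the question in a disputed death, and it does not say that the criterion then counts as met.

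A reader might also infer that deaths bypass the DSMB. They do not. The second limb of 9.2.4.4 asks only that the event be unexpected and thought related, with no *probably* threshold, and the expected-event lists in 10.3.1 show no fatal outcome. Under 9.1 the DSMB may recommend termination whatever the boundary shows. Deaths that are not unanticipated problems go to the Clinical Director within 7 days. Grading also refers to CTC version 4.0, so the four-row table may not be the whole scale. The text just before 9.2.4.1 was not available as read, so the reporting point carries that reservation.

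The EXTEND clots do not show that such events are barred from the count. Nothing says they were fatal or irreversible, and a clot that improves after stopping can reach *probably* through timing, dechallenge and known pattern.

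Finally, one could assume that half of all true events miss the threshold, which takes the stop probability at a true 40% rate from 93.9% to 22.4%. That share has no source and would cover reversible grade IV events, where the table works. The printed operating characteristics are correct for events that meet the 8.5 definition.

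**Conclusion.** The point holds in a limited form. For deaths and irreversible grade IV events, two attribution criteria cannot operate. *Definitely* is unattainable for a death, and *probably* then requires all three remaining criteria unless an ambiguous exception is used. New-type fatal toxicities and fatal clots in patients with risk factors are the cases likely to be missed.

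This rests on the 8.5 threshold, which the second quoted sentence of 9.2.3 supports. If the first governed, *possibly* related deaths would count and the gap would largely close, so the two sections must be reconciled in any case.

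The size cannot be estimated from the documents. The contrast of 57.9% with 22.4% depends on assumed rates, independence and the loss of every drug-related death. The notification gap is narrower: related deaths judged expected.

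**What to change.** 1. In 8.5 and 9.2.2, state that for deaths and irreversible grade IV events the dechallenge and recurrence criteria do not apply. Attribution then rests on timing, absence of another explanation and known pattern, with two of the three sufficing for *probably*, confirmed by the existing independent monitor. Under this rule the new-type toxicity and the clot with risk factors are counted; the disease-explained bleed or infection in the table above, which meets timing alone, is not.
2. Make 8.5 and both sentences of 9.2.3 give the same attribution threshold.
3. In 9.2.4.4, replace the first limb with: *all deaths and all events listed in 8.5, expected or not*.

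**Cost.** A few sentences and no new committee. Two of three is also the table's count for *possibly*, so for these events the two grades would differ only in the stated degree of certainty; the text should acknowledge this. A few more deaths may count, raising the chance of a precautionary stop. The rise is slight only if such deaths are rare: on the plan's own row, a counted rate of 25% instead of 20% moves stopping from 22.4% to 43.9%. The 20% benchmark should therefore be confirmed for the revised definition. Counting every *possibly* related event of any kind against an unchanged benchmark would be a larger trade-off and is not proposed.

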8.3 Sample Size

We intend to accrual a maximum of 38 subjects for this study. Because the efficacy of eltrombopag in this patient population is unknown, we would like to reject the treatment as quickly as possible with a small number of patients if the treatment is not effective. We will use the Two-Stage Minimax Design outlined in Table 1 of Simon ⁽¹⁾ with a response probability of 20% or less to terminate the treatment and the hypothesized actual response probability of 40% or more. The sample size is determined by testing the null hypothesis $H_0: p \leq 20\%$ versus the alternative $H_1: p \geq 40\%$ at a significance level of 0.05 and a power of 0.8. At the first stage, 18 subjects will be accrued and the trial will be terminated by accepting the null hypothesis if 4 or fewer subjects respond to the treatment within 16 to 20 weeks. If 5 or more subjects respond to the treatment within 16 weeks at the first stage, then an additional 15 subjects will be accrued at the second stage. If needed, the replacement of 5 drop-out subjects will bring the total number of subjects to $n=38$. The null hypothesis of $p \leq 20\%$ will be accepted (i.e., the drug will be rejected) if the total number of responders within 16 to 20 weeks is 10 or less. This sample size is calculated by the PASS power analysis and sample size software (NCSS, LLC., [name]).

Subjects who discontinue the study drug prematurely (before 16 weeks):

Platelet count measurement will be attempted even if a patient discontinues study drug. Patients who withdraw from the study for reasons other than lack of efficacy or toxicity (rendering platelet count missing) may be replaced. All other patients should be evaluable for efficacy. Based on the assumed drop-out rate of 15-20% and the goal of having 33 evaluable patients, 5 additional patients may be enrolled if needed.

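### Section 8.5: the last row of the safety stopping table runs one subject too long under the plan's own 90% rule, and the table and its simulation end at 33 although 38 subjects are allowed

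*Combined protocol and SAP*

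**What the plan says.** Section 8.5 monitors specified treatment-related serious adverse events (TRSAEs) with a Bayesian rule. The prior is Beta(0.72, 2.88), with mean 0.20. The boundary is reached when the posterior probability that the true rate "exceeds this benchmark rate of 20% is at least 90" per cent. On timing, the section says "we will start safety monitoring when 3 or more subjects have developed a TRSAE". The prior weight of 3.6, it says, "is approximately 15% of the expected sample size"; that sample size is not stated.

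The printed table reads: 3 events up to 5 subjects, 4 up to 9, 5 up to 13, 6 up to 16, 7 up to 20, 8 up to 24, 9 up to 28, and 10 up to 33. A simulation of 33 independent subjects follows. It gives stop proportions of 1.8%, 22.4%, 43.9%, 66.7% and 93.9% at true rates of 0.10, 0.20, 0.25, 0.30 and 0.40, with average numbers of subjects and of TRSAEs.

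Section 8.3 refers to "the goal of having 33 evaluable patients", but also says "We intend to accrual a maximum of 38 subjects for this study". The difference comes from replacements: "If needed, the replacement of 5 drop-out subjects will bring the total number of subjects to" 38.

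**The concern.** The rule and the table are two statements of one decision threshold, so they should agree at every sample size the study can reach. At 33 subjects they do not: the table stops at a count that falls just short of the stated posterior probability. From 34 to 38 subjects the table gives no threshold, and the reported operating characteristics do not cover that range. A monitoring board that sees 10 events at the 33rd subject, or any count after it, would have to choose between the formula and the table, or compute a threshold itself.

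**Working it through.** **Inputs.** Section 8.5: prior Beta(0.72, 2.88), benchmark 0.20, cut-off 0.90, the eight table rows, and the simulation results. Section 8.3: 33 evaluable subjects, maximum 38, first stage of 18 with termination at 4 or fewer responders.

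**Formula.** After x events in n subjects, the posterior probability is 1 − F(0.20), where F is the distribution function of Beta(0.72 + x, 2.88 + n − x). A row should end at the largest n for which this is at least 0.90.

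**Table against rule.**

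| Events | Printed row end | Posterior there | Posterior one subject later |
|---|---|---|---|
| 3 | 5 | 0.929 | 0.8944 |
| 4 | 9 | 0.912 | 0.8812 |
| 5 | 13 | 0.903 | 0.8758 |
| 6 | 16 | 0.920 | 0.8986 |
| 7 | 20 | 0.917 | 0.8968 |
| 8 | 24 | 0.915 | 0.8968 |
| 9 | 28 | 0.915 | 0.8977 |
| 10 | 33 | **0.8994** | 0.8822 |

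The first seven rows end exactly where the rule says. The eighth should end at 32 (10/32 gives 0.915). At 33 the rule needs 11 events (0.951). Continuing: 11/37 gives 0.901, 11/38 gives 0.886 and 12/38 gives 0.941, so 11 holds up to 37 and 12 is needed at 38. Carrying 10 forward to 38 would give only 0.799.

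**Stop probabilities.** An exact recursion over successive subjects reproduces the plan's stop proportions from the printed table to within 0.1 point, and then gives the corrected ones:

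| True rate | Plan | Printed table, 33 | Corrected, 33 | Corrected and extended, 38 |
|---|---|---|---|---|
| 0.10 | 1.8% | 1.85% | 1.84% | 1.9% |
| 0.20 | 22.4% | 22.4% | 21.6% | 23.2% |
| 0.25 | 43.9% | 43.9% | 42.3% | 46.1% |
| 0.30 | 66.7% | 66.6% | 64.5% | 69.6% |
| 0.40 | 93.9% | 93.9% | 92.8% | 95.4% |

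**Average number of subjects.** The same recursion on the printed table gives 32.55, 28.65, 24.78, 20.29 and 12.45. The plan states 24.7, 22.4, 20.3, 17.6 and 12.0. Two checks need no recursion:

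- At a true rate of 0.10 only 1.8% of studies stop, so the average is at least 0.982 × 33 = 32.4. It cannot be 24.7.
- Expected events equal the true rate times expected subjects. The stated averages imply 0.10 × 24.7 = 2.5 and 0.20 × 22.4 = 4.5 events, against the plan's own 3.2 and 5.7. The recomputed averages give 3.25 and 5.73.

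**Prior weight.** 3.6/33 = 10.9% and 3.6/38 = 9.5%. For the two-stage design, expected N is 18 + (1 − probability of early termination) × 15. At a response rate of 0.20 the early termination probability is 0.716, so expected N is 22.3 and 3.6 is 16.2% of it. At 0.40 the probability is 0.094, so expected N is 31.6 and 3.6 is 11.4% of it.

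**The case against.** The case for leaving the table alone is that the miss is 0.0006. It matters only for a study that first reaches the boundary with its tenth event at the 33rd subject, and it leans toward stopping. Because subject 33 is the last in the plan's model, the average number treated does not change. The stop proportions correctly describe the table as printed. The general rule yields a threshold at any n, and the extra five subjects are conditional replacements. All of this stands and limits the point to a minor one. Rounding, however, does not explain the row: the table excludes 6/17 (0.8986), 7/21 (0.8968), 8/25 (0.8968) and 9/29 (0.8977), which also round to 90%.

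A reader might infer something stronger: that the prior weight is also misstated, so that two figures defining the boundary are wrong. The documents do not support this. They do not say what the expected sample size is, and in a two-stage design the term has a standard meaning. Under the null response rate it is 22.3, and 16.2% of that is fairly called about 15%. The description also does not enter the calculation; the boundary is set by the two prior parameters, the 20% benchmark and the 90% cut-off. Even if 15% of 33 had been meant, giving Beta(0.99, 3.96), the strict boundary up to 33 subjects would differ only in the 5-event row, which would end at 12 instead of 13.

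**Conclusion.** The point holds as a minor correction. One printed threshold, 10 events at 33 subjects, contradicts the plan's stated rule, and there is no printed threshold or simulation for subjects 34 to 38. Correcting the row changes the stop probability over 33 subjects by at most about 2 percentage points across the plan's five true rates. The printed row is the more cautious of the two, so it does not weaken protection of subjects. Separately, the average-number-of-subjects row of the simulation table is inconsistent with the printed boundary and with the TRSAE row beneath it.

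The row-end result needs no assumption beyond the printed prior, benchmark and cut-off. The extension to 38 assumes that replaced drop-outs still count among the subjects in the experiment; Section 8.5 does not exclude them. The stop probabilities assume, as the plan's simulation does, independent subjects checked one at a time.

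**What to change.** In the Section 8.5 table, end the 10-event row at 32 subjects, then add 11 events up to 37 and 12 events at 38. Rerun the simulation on this boundary to 38 subjects; stop proportions should be close to 1.9%, 23.2%, 46.1%, 69.6% and 95.4%. Replace the average-number-of-subjects row with the rerun's values, and check that each average number of TRSAEs equals the true rate times the average number of subjects. Keep Beta(0.72, 2.88), and name the sample size to which the 15% description refers. The cost is a table and wording correction and one short simulation; the design, sample size and prior are unchanged.
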